12 SAFETY REPORTING AND ANALYSIS

12.1 SAFETY ANALYSES

Safety evaluations will be based on the incidence, intensity, and type of adverse events, as well as on clinically significant changes in the subject's physical examination, vital signs, and clinical laboratory results. Safety analyses will be performed using the safety population. Safety variables will be tabulated and presented. Exposure to trial treatment and reasons for discontinuation of trial treatment will also be tabulated.

12.2 ADVERSE EVENTS

Adverse event (AE) monitoring and reporting is a routine part of every clinical trial. The following list of AEs and the characteristics of an observed AE (Section 8.2) will determine whether the event requires expedited reporting in addition to routine reporting.

12.3 ADVERSE EVENT CHARACTERISTICS

CTCAE term (AE description) and grade: The descriptions and grading scales found in the revised NCI Common Terminology Criteria for Adverse Events (CTCAE) version 4.0 will be utilized for AE reporting. All appropriate treatment areas should have access to a copy of the CTCAE version 4.0. A copy of the CTCAE version 4.0 can be downloaded from the CTEP web site http://ctep.cancer.gov/protocolDevelopment/electronic_applications/ctc.htm.

‘Expectedness’: AEs can be ‘Unexpected’ or ‘Expected’ for expedited reporting purposes only.

12.4 PROTOCOL-SPECIFIC EXPEDITED ADVERSE EVENT REPORTING EXCLUSIONS

There are no exclusions for expedited adverse event reporting. All adverse events, including death, will be considered unexpected and subject to expedited reporting.

12.5 ADVERSE EVENTS

All AEs and SAEs occurring on trial will be listed by subject. The frequency and percentages of subjects with treatment-emergent adverse events (TEAEs) will be tabulated by system organ class (SOC) and PT, where treatment-emergent is defined as any AE that:

- Occurs after first dosing of trial medication and through the end of the trial or up through 30 days after the last dose of trial treatment, or
- Is considered treatment-related regardless of the start date of the event, or
- Is present before first dosing of trial medication but worsens in intensity or the investigator subsequently considers treatment-related.

TEAEs that are considered at least possibly related to trial treatment will be tabulated as well as deaths, SAEs, and events resulting in treatment discontinuation.

AEs that occur after informed consent but before first dosing of trial medication will not be summarized but will be listed.

At each level of summarization, a subject will be counted only once for each AE, SOC, or PT experienced within that level. In the summation for AE severity, within each level of AE, SOC, or PT experienced, the one with the highest severity will be included. In the summation for AE's

relationship to the trial drug, within each level of AE, SOC, or PT experienced, the one with the closest relationship to the trial drug will be included.

12.6 DEFINITIONS OF ADVERSE EVENTS

An adverse event (AE) is any untoward medical occurrence in a subject or clinical investigation subject administered a pharmaceutical product. An AE does not necessarily have to have a causal relationship with this treatment. An adverse event (AE) can therefore be any unfavorable and unintended sign (including an abnormal laboratory finding, for example), symptom, or disease temporarily associated with the use of a medicinal product, whether or not considered related to the medicinal product. This includes any occurrence that is new in onset or aggravated in severity or frequency from the baseline condition.

In clinical studies, an AE can include an undesirable medical condition occurring at any time, including run-in or washout periods, even if no trial treatment has been administered. The NCI Common Terminology Criteria for Adverse Events (CTCAE) v4.0 is to be used for the grading of severity of symptoms and abnormal findings. For adverse events not covered by the NCI-CTCAE Version 4.0 grading system, the following definitions will be used:

- **Grade 1:** Mild; asymptomatic or mild symptoms; clinical or diagnostic observations only; intervention not indicated.
- **Grade 2:** Moderate; minimal, local or non-invasive intervention indicated; limiting age-appropriate instrumental ADL*.
- **Grade 3:** Severe or medically significant but not immediately life-threatening; hospitalization or prolongation of hospitalization indicated; disabling; limiting self-care ADL**
- **Grade 4:** Life-threatening consequences; urgent intervention indicated.
- **Grade 5:** Death related to AE.

The Investigator must also assess the relationship of any adverse event to the use of trial drug, based on available information, using the following guidelines:

- **Not Related:** Clear-cut temporal and/or mechanistic relation to a cause other than the trial drug.
- **Doubtful:** There is no reasonable possibility that the event is related to the trial drug but a definite cause cannot be ascertained.
- **Possible:** There is still a reasonable possibility that the cause of the event was the trial drug but there exists a more likely cause of the event such as complications of progressive disease.
- **Probable:** The most likely cause of the event is the trial drug but other causes cannot be completely excluded.
- **Definite:** Clear cut temporal and/or mechanistic relation to the trial drug. All other causes have been eliminated. Events classified as definite will often be confirmed by documenting resolution on discontinuation of the trial drug and recurrence upon resumption.

12.6.1 Recording of Adverse Events

All adverse events of any subject during the course of the trial will be reported on the case report form, and the investigator will give his or her opinion as to the relationship of the adverse event to trial drug treatment (i.e., whether the event is related or unrelated to trial drug administration). If the adverse event is serious, it should be reported as soon as possible and no greater than 24 hours

to TG Therapeutics and the Chair of DSMB. The Johns Hopkins IRB must also be notified as required by Johns Hopkins IRB guidelines. Other untoward events occurring in the framework of a clinical trial are also to be recorded as AEs (i.e., AEs that occur prior to assignment of trial treatment that are related to a protocol-mandated intervention, including invasive procedures such as biopsies, medication washout, or no treatment run-in).

All AEs regardless of seriousness or relationship to ublituximab treatment spanning from the signature of the informed consent form, until 30 calendar days after discontinuation or completion of protocol-specific treatment as defined by the protocol for that subject, are to be recorded on the CRF.

12.6.2 Abnormal Laboratory Values and Vital Signs

The reporting of abnormalities of vital signs as adverse events should be avoided. Abnormalities of vital signs should not be reported unless any criterion for an SAE is fulfilled, the vital signs abnormalities cause the subject to discontinue trial treatment, or the investigator insists that the abnormality should be reported as an AE. Any grade 3 or 4 laboratory abnormality or any clinically significant grade 1 or 2 hematology or biochemistry laboratory value(s) should be recorded as an AE. If an abnormal laboratory value or vital sign is associated with clinical signs and/or symptoms, the sign or symptom should be reported as an AE, and the associated laboratory value or vital sign should be considered additional information that must be collected on the relevant CRF.

Clinical Laboratory Results will be summarized. Summary statistics for actual values and for changes from baseline will be tabulated for laboratory results by scheduled visit. Subjects with laboratory values outside of the normal reference range at any post-baseline assessment will be summarized, and graded per NCI CTCAE Version 4.0 when applicable. Subject incidence of laboratory toxicity will be summarized and assigned a maximum grade for each laboratory test.

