3 SUBJECT SELECTION

3.1 ELIGIBILITY CRITERIA

Subjects eligible for enrollment must meet all of the following criteria:

1. Able and willing to provide written informed consent.
2. 18-100 years of age.
3. New acute optic neuritis and/or transverse myelitis. A new clinical event is defined as a clinically significant neurologic deficit(s) on physical exam, not attributable to another disease process, which is different from baseline neurological exam, and attributable to a lesion in the spinal cord, optic nerve or brainstem. New symptoms must be reported within 10 days of onset.
4. Highly suspected or confirmed diagnosis of NMO according to the 2006 revisions of the Wingerchuk diagnostic criteria for NMO (Wingerchuk, 2006), or AQP4 positive NMOSD per the EFNS Guidelines. For NMO, subjects must have two absolute criteria:
 - a. optic neuritis
 - b. myelitis

and at least two of three supportive criteria:

- c. presence of a contiguous spinal cord MRI lesion extending over three or more vertebral segments,
- d. MRI criteria NOT satisfying the revised McDonald diagnostic criteria for MS [Polman, 2011]
- e. NMO-IgG (AQP4) in serum.

For NMOSD, subjects must have longitudinally extensive transverse myelitis (LETM) recurrent isolated optic neuritis (RION)/bilateral optic neuritis (BON), or opticospinal multiple sclerosis (OSMS) that is AQP4 antibody positive

5. The B cell count must be normal (5-20% of total lymphocytes) in subjects who have not received another B cell depleting therapy in the past year. For those on B cell depleting therapy within the past year, a B cell count of at least 0.5% of total lymphocytes is necessary.
6. A female subject is eligible to enter the trial if she is:
 - a. Not pregnant or nursing;
 - b. Of non-childbearing potential (i.e. women who have had a hysterectomy, are post-menopausal, which is defined as >2 years without menses or, in female subjects who have been post-menopausal for <2 years, must be confirmed with Follicle Stimulating Hormone (FSH) and estradiol levels), have both ovaries surgically removed or have current documented tubal ligation)

OR

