 - b. Non-invasive basal cell and squamous cell skin carcinoma
 - c. Cancer diagnoses with a duration of complete response (remission) >5 years

A history of hematologic malignancy excludes a subject from participation, regardless of response.

5. Absolute neutrophil count less than 1000/microliter *or* platelet count less than 50,000/microliter of blood.
6. Significant concurrent, uncontrolled medical condition including, but not limited to, cardiac, renal, hepatic, hematological, gastrointestinal, endocrine, immunodeficiency syndrome, pulmonary, cerebral, psychiatric, or neurological disease which could affect the subject's safety, impair the subject's reliable participation in the trial, impair the evaluation of endpoints, or necessitate the use of medication not allowed by the protocol, as determined by the PI of the trial.
7. Use of an investigational drug or other experimental therapy for a condition other than NMO within 4 weeks, 5 pharmacokinetic half-lives or duration of biological effect (whichever is longer) prior to screening.
8. Current participation in any other interventional clinical trial. Participation in non-interventional trial requires approval of the protocol by investigator.
9. Subjects who are concurrently receiving any other investigational agents, or have participated in an interventional clinical trial within the last 21 days, or subjects who have been vaccinated with a live vaccine < 2 months prior to trial inclusion.
10. Because there is an unknown but potential risk for adverse events in nursing infants secondary to treatment of the mother with ublituximab breastfeeding should be discontinued if the mother is enrolled.

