6 DOSING DELAYS/DOSE MODIFICATION

A single dose of 450 mg of ublituximab will be administered under the direction of the Principal Investigator, [name] while the subject is in the hospital. It is required that the absolute neutrophil count be $\geq 1000/\mu\text{L}$ and the platelet count be $\geq 50,000 \mu\text{L}$ before the infusion. If the liver enzymes (ALT and/or AST) are > 5 times the upper limit of normal (ULN) of the normal range at the John Hopkins medical laboratory or if the neutrophil count and platelets counts are below acceptable levels as described, the dose of ublituximab will be held for up to 48 hours until the laboratory values return to within acceptable range. If all labs above do not return to within acceptable range within 48 hours, the subject will not receive the ublituximab infusion and will be withdrawn from the study.

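### The laboratory toxicity count in Section 12.6.2 ignores the pre-infusion value, so an unchanged abnormality is counted as toxicity

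*Combined protocol and SAP*

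**What the plan says.** Section 12.6.2 plans three laboratory outputs.

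- A numeric summary: "Summary statistics for actual values and for changes from baseline will be tabulated for laboratory results by scheduled visit".
- A count of subjects: "Subjects with laboratory values outside of the normal reference range at any post-baseline assessment will be summarized", graded under CTCAE version 4.0 where that applies.
- A toxicity incidence: "Subject incidence of laboratory toxicity will be summarized and assigned a maximum grade for each laboratory test".

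Only the first refers to baseline, and it gives statistics by visit, not subject counts. The section plans no table of grade before against grade after, and it does not define the laboratory baseline.

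The limits on what may be present at infusion are in two places. Exclusion item 5 under Section 3.1 bars subjects only at "Absolute neutrophil count less than 1000/microliter" or "platelet count less than 50,000/microliter of blood". Section 6 repeats those limits before dosing and adds a hold for liver tests: "If the liver enzymes (ALT and/or AST) are > 5 times the upper limit of normal (ULN").

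The adverse event rules are worded differently. Section 12.6 says of adverse events: "This includes any occurrence that is new in onset or aggravated in severity or frequency from the baseline condition". Section 12.5 treats an event present before dosing as treatment-emergent if it intensifies or the investigator later judges it related. Section 12.11.5 makes a pre-existing condition an AE only if it worsens. Sections 12.6.2 and 12.11.2 also require grade 3 or 4 laboratory abnormalities, and clinically significant lower grades, to be recorded as AEs, without repeating a baseline condition.

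**The concern.** A toxicity incidence is normally read as something that arose or worsened after treatment. Here a subject who enters with mildly raised ALT and keeps the same ALT throughout appears in the table exactly like a subject whose ALT was normal and then rose to that level. The table cannot separate them.

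This cuts against the plan's own approach. Section 12.1 bases safety evaluation on clinically significant changes in laboratory results, and Sections 12.5, 12.6 and 12.11.5 refer to worsening. The subject-level laboratory count is the exception.

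The tests concerned are not peripheral. Neutropenia, thrombocytopenia and raised liver enzymes are three of the four event types that Section 13 asks the DSMB to follow, and they are the tests for which the plan expressly tolerates an abnormal starting value. With five subjects, one misplaced count moves a percentage a long way.

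There is a smaller ambiguity at data entry. Staff who read only the laboratory-AE sentences could record an unchanged abnormality as an AE; staff who read Section 12.11.5 would not.

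**Working it through.** The plan states no figure for this count, so there is none to reproduce. The check sets the rules side by side and then sizes the effect.

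**1. Can a subject be infused with an out-of-range value?**

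| Test | Permitted at infusion | Source |
|---|---|---|
| ALT/AST | up to 5 times ULN | Section 6 (dosing hold, not an entry criterion) |
| Neutrophils | from 1000/microliter | Section 3.1, exclusion item 5; Section 6 |
| Platelets | from 50,000/microliter | Section 3.1, exclusion item 5; Section 6 |

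For ALT/AST the answer is yes by definition, since anything between 1 and 5 times ULN is out of range. For neutrophils and platelets it is yes provided the laboratory's lower limits of normal lie above 1000 and 50,000. The documents do not print those limits, so this is an assumption.

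**2. Does the count then include an unchanged value?** The out-of-range rule looks only at post-baseline assessments. An abnormal value that persists unchanged meets it. Laboratory toxicity is not separately defined; taking it to mean the graded out-of-range values is the natural reading of adjacent sentences.

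**3. How far can carry-over reach?** Section 6 bars infusion with neutrophils below 1000, platelets below 50,000 or ALT/AST above 5 times ULN. A later value beyond one of these limits must be worse than the value that permitted dosing. For these tests, carry-over is therefore confined to milder abnormalities inside the limits.

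**4. Size.** Safety analyses use all dosed subjects (Section 11.3), so n = 5 if all five are infused. Each subject counted only for an unchanged abnormality adds 1/5 = 20 percentage points to that test. At n = 4 it adds 1/4 = 25 points. Illustrations, with exact (Clopper-Pearson) 95% intervals:

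| Truly worsened | Unchanged abnormality | As written | Counting worsening only |
|---|---|---|---|
| 0 | 1 | 1/5 = 20% (0.5% to 71.6%) | 0/5 = 0% (0% to 52.2%) |
| 0 | 2 | 2/5 = 40% (5.3% to 85.3%) | 0/5 = 0% (0% to 52.2%) |
| 1 | 1 | 2/5 = 40% (5.3% to 85.3%) | 1/5 = 20% (0.5% to 71.6%) |

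**5. How likely is at least one such starting value?** The documents do not give the share p of subjects with a permitted abnormality before infusion. For an assumed p, the chance that at least one of five has one is 1 − (1 − p)^5:

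- p = 10%: 1 − 0.9^5 = 41%
- p = 20%: 1 − 0.8^5 = 67%
- p = 30%: 1 − 0.7^5 = 83%
- p = 50%: 1 − 0.5^5 = 97%

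This is the chance of an abnormal starting value. The count is inflated only if that value persists without worsening.

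**The case against.** The case for leaving the table alone has several parts.

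*It is not the primary safety result.* This stands. A reader might infer that the trial's main safety finding is contaminated. The synopsis and Section 11.2 define the safety summary as subjects with any AE, any SAE, AEs leading to discontinuation and drug-related AEs. The laboratory table supports it, and Sections 12.5 and 12.11.5 largely protect the AE counts.

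*The DSMB will not be misled.* This also stands. The synopsis has the DSMB review raw data from the database, first on two subjects and later on three more. Nothing indicates that it would act on the end-of-study incidence table.

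*Worsening remains visible elsewhere.* Partly true. Changes from baseline are summarized by visit, Section 11.2 provides listings sorted by subject, and five courses can be read individually. None of this corrects the reported incidence.

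*The formal SAP will settle it.* Section 11 promises further detail before database lock, but the available text contains no baseline condition. In an open-label study, a rule fixed that late could be chosen with the results in view.

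*The rule errs towards over-reporting.* For the count, yes. It also makes a new abnormality look the same as an old one of equal grade.

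A further inference is tempting: "For those on B cell depleting therapy within the past year, a B cell count of at least 0.5% of total lymphocytes is necessary", while 5-20% is called normal, so such subjects seem to inflate the toxicity count from the start. The documents do not support this. B-cell depletion is the intended effect with its own objective (Section 2.2), and Section 1.4 expects most, if not all, circulating B cells to be gone by about day 5 whatever the starting count. No section calls it laboratory toxicity.

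**Conclusion.** The point holds in a limited form. As written, Section 12.6.2 counts an unchanged pre-infusion abnormality as laboratory toxicity, while the plan's AE rules look to worsening. One such subject among five would shift a test's incidence from 0/5 to 1/5, or 20 percentage points. Whether there will be any such subject is unknown, and the figures above are illustrations under stated assumptions.

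A reader might go further and see a contradiction between the laboratory and AE rules. That is too strong: they are separate outputs, and a table of values may serve a different purpose from a table of events. The weakness is that the laboratory output is labelled as toxicity incidence but lacks the baseline reference the label implies.

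The effect is confined to a descriptive supporting table and, for the three tests with limits, to abnormalities inside those limits. It is worth correcting because doing so is cheap, but it is not a must-fix.

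**What to change.** In Section 12.6.2, or in the formal SAP before any data are summarized:

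1. Define laboratory baseline as the last value before the infusion. This matters because Section 5.3 lets steroids start at an outside hospital beforehand, so different pre-infusion samples may not be interchangeable.
2. Count treatment-emergent laboratory toxicity only when the post-infusion CTCAE grade exceeds the baseline grade, or when a normal value becomes abnormal.
3. Add, for each test, a table of baseline grade by worst post-infusion grade.
4. List unchanged pre-existing abnormalities separately.
5. State that the laboratory-AE sentences in Sections 12.6.2 and 12.11.2 follow the worsening principle of Sections 12.5, 12.6 and 12.11.5.

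The cost is wording and table shells. Section 7 already calls for a blood count and metabolic panel before infusion, and no dosing or clinical rule changes. Reported incidences may look slightly more favourable, so the rule should be fixed early. Worsening within a grade would drop out of the count, so the planned change-from-baseline summaries and subject listings should stay.

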12.6.3 Handling of Adverse Events

All adverse events resulting in discontinuation from the trial should be followed until resolution or stabilization. Subjects must be followed for AEs for 30 calendar days after discontinuation or completion of protocol-specific treatment. All new AEs occurring during this period must be reported and followed until resolution unless, in the opinion of the investigator, these values are not likely to improve because of the underlying disease. In this case, the investigators must record his or her reasoning for this decision in the subject's medical record and as a comment on the CRF. After 30 days, only AEs, SAEs, or deaths assessed by the investigator as treatment related are to be reported.

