2.1 PRIMARY OBJECTIVES

To assess safety of acute B cell depletion in NMO subjects with acute relapse of optic neuritis or transverse myelitis who are treated with ublituximab + steroids beginning on dose administration and ending with repletion of circulating B cells.

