5.4 DURATION OF FOLLOW UP

After discharge from the hospital, subjects will be followed as an outpatient clinically at days 90 and 180. In addition, subjects will be monitored monthly for B cell counts for as long as it takes for B cells to replete to a minimum of 0.5% for patients who will continue to be treated with B-cell depleting agents for preventive care, according to standard of care, or to a minimum of 5% for patients who will use other preventive strategies. For most subjects, the duration of B-cell depletion with UTX is up to 9 months. Subjects removed from the trial for unacceptable adverse event(s) will be followed until resolution or stabilization of the adverse event. In addition, subjects will be checked by complete blood count with differential and complete metabolic profile for evidence of toxicity to other cells (e.g., neutrophils) or organs such as kidney or liver function.

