
Follow-up

The primary outcome is safety for the duration of the period of B cell depletion. Secondary efficacy outcomes will be assessed at follow up 90 and 180 days after initial hospitalization for the acute relapse. In addition to a thorough history and physical examination, including EDSS rating, visual examination and timed walk, a research MRI of the spine will be performed at day 90 to compare to the relapse lesion. In addition, subjects will be sent to a local lab for monthly CD19 monitoring until the B cell counts replete to a minimum of 0.5% for patients who will continue to be treated with B-cell depleting agents for preventive care, according to standard of care, or to a minimum of 5% for patients who will use other preventive strategies. These results will be reviewed by the PI, [name].

Withdrawal

For subjects who discontinue or withdraw from the trial, investigators will continue to monitor subjects who have ongoing neurologic deficits while the subject remains in the hospital. This involves periodic neurologic exams and close observation in collaboration with the treating physician.

Subjects unable to tolerate ublituximab will be withdrawn from the trial. A tolerability issue for the purpose of withdrawing to alternative treatment is defined as a moderate or severe side-effect or complication related to treatment, which is unacceptable to the subject; or a clinically significant change in hematologic, hepatic, or renal laboratory parameters that, in the opinion of the investigator, would require a change in treatment.

Definition of Completer and Maximum Duration of Participation

A completer is defined as a subject who has completed all of the clinically necessary phases of the trial, as per standard of care, and has followed up in the NMO Clinic for all follow up visits. The maximum duration of participation is up to 9 months for most subjects.

Magnetic Resonance Imaging in the Trial

The trial will utilize MRI for spine imaging with and without contrast during the trial for relapses, as per standard of care and for research purposes on 90-day follow-up. In cases of poor creatinine clearance, contrast will not be used. According to standard of care, MRI scans in the trial will be performed at the initiation of the relapse. On follow up, the MRI is a research procedure. For purposes of this trial, standard of care MRIs of the spine will be reviewed by trial staff; the following characteristics will be recorded for research purposes:

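### Recording of adverse events of any cause ends 30 days after treatment under Sections 12.6.1 and 12.6.3, but the primary safety outcome runs to B-cell repletion

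*Combined protocol and SAP*

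**What the plan says.** **Window of the primary outcome.** Section 2.1 sets the safety assessment as "beginning on dose administration and ending with repletion of circulating B cells". Section 7 (Follow-up) agrees: "The primary outcome is safety for the duration of the period of B cell depletion". Section 5.4 gives the expected length, "For most subjects, the duration of B-cell depletion with UTX is up to 9 months", and sets no fixed end: "subjects will be monitored monthly for B cell counts for as long as it takes for B cells to replete". It defines repletion as at least 0.5% or at least 5% B cells, depending on the later preventive strategy.

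**Narrow recording rules.** The last paragraph of Section 12.6.1 has events of any cause entered on the CRF from consent "until 30 calendar days after discontinuation or completion of protocol-specific treatment". Section 12.6.3 adds: "After 30 days, only AEs, SAEs, or deaths assessed by the investigator as treatment related are to be reported".

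**Wider rules.**
- Section 12.6.1 opens with "All adverse events of any subject during the course of the trial will be reported on the case report form".
- Section 12.5 says "All AEs and SAEs occurring on trial will be listed by subject". Its treatment-emergent definition gives two alternative end points, the end of the trial or 30 days after the last dose, and does not choose.
- Section 12.7.2 has the sponsor told of every SAE whatever its cause, next to a period reaching through 9 months of follow-up. A later paragraph of the same section uses 30 days.
- Section 12.9 puts all AEs on the AE form and names no time limit.
- Section 12.11.3 has every on-trial death reported whatever its attribution, although its preceding sentence speaks of attributed deaths up to 30 days after the dose.
- Section 13 has AEs outside the DSMB's list documented, serious or not.
- Table 6 (Section 9) marks adverse-event assessment at Days 90 and 180.

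The Synopsis (Safety Endpoints) refers only to the treatment period. The primary safety summary (Synopsis, Statistical issues; Section 11.2) counts subjects with any AE and any SAE, and counts drug-related AEs separately.

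**The concern.** A summary of any AE over the depletion period needs events of any cause over that period. The narrow rules stop collecting them early and then let in only what the investigator attributes to treatment. Whether late events are related to ublituximab is part of what a safety study is meant to find out, and here the attribution is made by someone who knows that every subject received the drug.

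The same event is therefore kept or left out depending on which sentence is followed. Take a non-serious infection on Day 120 that is judged unrelated. The opening of Section 12.6.1, the listing in Section 12.5 and Section 12.9 keep it. The last paragraph of Section 12.6.1 and Section 12.6.3 do not. Two members of staff, each following the protocol in good faith, could build different primary datasets. The AE-frequency objective in Section 2.2 and the tables by system organ class and preferred term carry the same uncertainty.

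**Working it through.** **1. No planned figure to reproduce.** The 5 subjects are set by feasibility (Section 11.1), with no event rate or power behind them. The check is calendar arithmetic plus a comparison of the rules.

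**2. Inputs.** Ublituximab is given on Day 1 and the last steroid dose on Day 5 (Section 5.3). Plasma exchange, if needed, runs to Day 20 (Table 6). The recording limit is 30 days after protocol-specific treatment (Section 12.6.1), and the documents do not say which of these treatments that term covers. Depletion lasts up to 9 months for most subjects (Section 5.4), taken as 270 days because the last scheduled monthly laboratory test is on Day 270.

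**3. Share of the window with all-causality recording.** Cut-off = last treatment day + 30. Share = cut-off / length of depletion.

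| Treatment ends with | Cut-off | Share of 270 days | Days left | Share of 180 days |
|---|---|---|---|---|
| Ublituximab, Day 1 | 1 + 30 = Day 31 | 31/270 = 11.5% | 270 - 31 = 239 | 31/180 = 17.2% |
| Steroids, Day 5 | 5 + 30 = Day 35 | 35/270 = 13.0% | 270 - 35 = 235 | 35/180 = 19.4% |
| Plasma exchange, Day 20 | 20 + 30 = Day 50 | 50/270 = 18.5% | 270 - 50 = 220 | 50/180 = 27.8% |

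The 180-day column is an assumption: the lower end of the 6 to 8 months that Section 1.4 gives for rituximab. It is not a floor. Section 1.4 says that plasma exchange may shorten depletion, and the 0.5% threshold is reached sooner than the 5% one.

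**4. An event after the cut-off that is judged unrelated.**

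| Event | Sections 12.6.1 (end) and 12.6.3 | Other text |
|---|---|---|
| Grade 3 or 4, or clinically significant, laboratory value | Left out | Recorded as an AE, with no time or attribution limit (12.6.2, 12.11.2); blood count and metabolic profile are monthly (Synopsis, Follow-up) |
| SAE | Left out | Sponsor notified whatever the cause (12.7.2), but that section also has a 30-day paragraph |
| Death | Left out | All on-trial deaths reported (12.11.3) |
| Non-serious clinical event, such as an infection | Left out | Kept by the general wording of 12.6.1 (opening), 12.5 (listing) and 12.9; Section 13 has infections followed by the DSMB and other AEs documented. No rule specific to such late events protects them |

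The last row has the least protection. Of the four event types that the DSMB follows (Section 13), neutropenia, thrombocytopenia and liver-enzyme elevation are measured by the monthly tests. Infection is not.

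**5. Scheduled contacts.** There are 9 monthly tests, on Days 30 to 270. Days 90 and 180 are already AE visits, and both fall after every cut-off in step 3. That leaves 9 - 2 = 7 monthly contacts without a planned AE enquiry, or 7 x 5 = 35 for 5 subjects.

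**The case against.** The best case for the plan is that late events are largely covered already. AE assessment is scheduled at Days 90 and 180, with history and examination (Table 6, Section 7), so a late infection can come to light. Laboratory abnormalities become AEs without any time limit. SAEs and deaths have explicit all-causality text, and Section 12.6.3 keeps every event judged related. The study is small and descriptive, with listings by subject. Section 12.6.3 can also be read as a rule on reporting rather than recording. The formal SAP that Section 11 announces and the Safety Monitoring Plan are not part of these documents and may settle the matter.

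Most of this stands, and it narrows the point. It rules out some stronger readings that a reader might infer:
- That more than four fifths of the safety information is lost. The shares in the table are of calendar time, and the documents give no timing of unrelated events.
- That after the cut-off the any-AE row can hold only related events. Sections 12.6.2 and 12.11.2 bring in laboratory abnormalities whatever the attribution.
- That the late events of the earlier CLL study (Section 1.2: 12 infections, 4 neutropenias) measure the loss. There, late means more than one week after the last infusion, so some may fall within 30 days. All were drug related, and Section 12.6.3 keeps related events.
- That an uncounted SAE among 5 subjects shows the typical effect. SAEs are among the best-protected events and are exposed only through the conflict between sections.

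What does not stand is the reading that no rule limits recording: the end of Section 12.6.1 sets the 30 days expressly for the CRF. Nor can an SAP restore events that were never collected. The Day 90 and 180 visits sharpen the conflict, since staff would ask about events that Section 12.6.3 excludes unless they are judged related.

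**Conclusion.** The point holds. The primary outcome window and the narrow recording rules do not match, and the protocol's own sections disagree on which events are kept after 30 days. Under the narrow rules, all-causality recording covers 11.5% to 18.5% of a 270-day depletion period, and more if depletion is shorter (17.2% to 27.8% at an assumed 180 days). The Day 50 reading applies only to subjects who have plasma exchange.

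The main exposure is late non-serious clinical events judged unrelated. SAEs and deaths are at risk only if staff follow Section 12.6.3 over Sections 12.7.2 and 12.11.3. The number of events affected cannot be worked out from the documents, and the any-AE percentage might change little if early infusion-related events already count most subjects. A dataset collected under Section 12.6.3 could still be reported, but not as all-causality safety over the depletion period. Because missed events cannot be recovered at analysis, this needs settling in the protocol before data are collected.

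**What to change.** Reconcile the Synopsis (Safety Endpoints), Table 6 and Sections 12.5, 12.6.1, 12.6.3, 12.7.2, 12.9 and 12.11.3 into one data-collection rule, and confirm that Sections 12.6.2 and 12.11.2 agree with it:
- Record all AEs, SAEs and deaths, whatever the attribution, from consent through documented B-cell repletion as Section 5.4 defines it. Events before dosing are listed only, as Section 12.5 already provides.
- Reconcile that end with the 9-month figures in the Synopsis (Duration of Subject Participation), Section 7 (maximum participation) and Section 12.7.2.
- Use the same window, dosing to repletion, for the treatment-emergent definition, in place of the two alternatives in Section 12.5, and for the primary safety summary.
- Report attribution as a descriptor, not as a condition for recording.
- Flag events that start after another B-cell-depleting agent is given.
- Add a brief AE enquiry at the monthly laboratory contacts that are not already AE visits.
- Keep expedited-reporting timelines separate.

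No dose or treatment rule changes. The cost is amendment wording, about 7 short calls per subject through Day 270 (up to 35 for 5 subjects; fewer if repletion is earlier, more if later), more CRF entries and possibly higher reported AE counts.
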